10.0 Study Design / Methods

This is a prospective randomized 4-6 weeks clinical trial with patients randomized 1:1 between SYNC and Non-SYNC TMS. Non-SYNC TMS is FDA approved and it is unlikely that SYNC TMS will be less effective than current practice. There is thus no sham or placebo control condition in this study, and all subjects are likely to benefit clinically. The MRI scanning session pre-TMS treatment will be split into 2 sessions. Visit 1 should take approximately 45 minutes with the whole time in the MRI scanner. Visit 2 should take approximately 180 minutes with 90 minutes in the MRI scanner. If the post-TMS treatment MRI is completed, the visit will last approximately 3 hours.

There is only one phase of this clinical trial.

All procedures are research only and there are no clinical procedures being performed.

The SYNC and NON-SYNC treatment groups will receive the following dose of rTMS delivered over the left prefrontal cortex: 6-13 Hz, 120% Motor Threshold*, 40 pulses per train, 3-7 second pulse train, 6-14 second intertrain (IT) interval **, 3000 pulses per session, one session per weekday.

This will initially be delivered for a fixed 4-week interval. For those individuals showing some degree of clinical response (defined as percentage change in HDRS score from baseline >25%), they will continue getting their initial treatment (SYNC or NON-SYNC) up to 6 weeks total. [*Although the treatment will be administered at 120% of Motor Threshold, the treatment course will have a ramp up period with the first treatment at 100% of Motor Threshold and the second treatment at 110% Motor Threshold]

We will differentiate the two groups solely on whether the TMS pulses are applied at an individual's phase optimum (individual alpha frequency (IAF) phase locked) or not. The two groups will both have rTMS applied at the individual's IAF (this is done because if the rTMS pulse train is at a different frequency it will no longer be at the correct phase after less than ¼ of the 4 second train) but in one group the initial TMS pulse will be phase-locked to the individual's optimum (as determined by a prior EEG/TMS/fMRI study using the instrument developed in the R21) and in the other group the TMS pulse will be applied at a random phase. The only difference between the two groups is the phase-locking of the pulse train. This active phase-locked condition is designed to maximize the target engagement we have demonstrated by increasing the response in the ACC so as to increase the likelihood of a stronger clinical antidepressant effect. By doing this we will be able to demonstrate whether applying rTMS at an optimum phase has a larger clinical effect on remission rates. If there are substantial clinical differences between the two groups, then we know that phase locking of rTMS to the optimum phase has a demonstrable antidepressant clinical effect.

Interruptions - Every attempt shall be made to complete each treatment session as per the protocol. Interruptions during the treatment are allowed as needed for patient comfort or convenience by using the "pause" selection on the device. However, an incomplete treatment will be recorded. In the event that a treatment is missed: 1 or 2 days missed, continue into the subsequent week to complete the missed days. Evaluation should still occur after every 5 treatments. 3 or more days in a row – treatment must be aborted and the subject discontinued from their current phase and likely dropped from the study.

Evaluation After Every 5 Treatment Sessions and at the end of the 4th week. The Inventory of Depression and Anxiety (IDAS) will be assessed at the baseline and at the end of treatment course. Brief COVID-19 questionnaires will be used to assess perceived threat, impact and experiences assessed at baseline, end of treatment and in follow-ups. At the end of each week of treatment, or after every five treatment sessions, patients will have the following assessments performed by a qualified individual who is masked to the subject's assigned treatment group:

Hamilton Depression Score (Ham-D 28 item),

Inventory of Depressive Symptomatology Self-Report (IDS-SR),

Montgomery-Asberg Depression Rating Scale (MADRS),

Global Assessment of Functioning (GAF),

Clinical Global Impression (CGI).

(Upload in eIRB all surveys, scripts, etc.) Include what data will be collected.

[figure not shown]
11.0 Specimen Collection and Banking (if applicable)

 The only specimens will be MRI scans before and after treatment, EEG data and rating forms.

12.0 Data Management

Describe the data analysis plan, including any statistical procedures.

Remember that the R33 clinical trial is not meant to be a definitive trial of SYNC rTMS.

Rather, it is designed to test whether synchronization of the TMS pulse with the subject's brain activity produces a markedly better response than the current approach to treatment, which is NON-SYNC. We thus reason that we need to see a clinically meaningful additional remission rate with SYNC versus NON-SYNC, in order for future definitive trials to be conducted. MRI scanning is expensive and having

TMS machines that sync with the patient's EEG are more complex and expensive than the current methods. We thus are powered in this R33 to detect a very large effect size (0.65).

The best trials of daily left prefrontal rTMS with focal figure eight coils are the industry sponsored Neuronetics trial, and the OPT-TMS trial. With inclusion and exclusion criteria very similar to the current trial, in the open label phases, they each achieved about a 30% remission rate. Published remission rates for ECT in a similar population in open label studies are roughly 60%. This current trial, although there is a randomization, are more like open label studies in that all subjects will be told they are getting some form of TMS. Fig 1D shows that consenting 60 subjects to get 50 completers has a .95 power of detecting this large of a difference, using a

simple chi-square comparison of remitters across the two groups. An additional aspect of the proposed clinical trial will be to provide researchers with the exact differences in remission, if there are any. Those can be integrated with future refinements and developments of rTMS. Thus, even if the effect size difference is not terribly large, one may wish to perform SYNC TMS in initial NON-SYNC responders. Moreover, we will examine the imaging and demographic variables to potentially identify response predictors that might guide future work.

- 2) Intent-to-treat, completer and fully adherent samples: The main analysis will focus on the intent-to-treat (ITT) sample. The ITT sample is defined as all randomized patients who receive at least 1 rTMS clinical treatment. Secondary analysis will be performed on two sub-samples: (a) completer sample and (b) fully adherent sample. The completer sample comprises patients who are evaluated after 4 weeks of treatment or terminate (and are evaluated) sooner based on investigator judgment that maximal clinical improvement had been obtained (regardless of remission status). In other words, completers are those patients in whom the maximal number of treatments was given or who terminate sooner due to the judgment that further treatment will not result in additional improvement (and who completed the 4 week fixed dose period). Patients who terminate the study early for any other reason [eg, withdrawal of consent, adverse event, etc.] do not contribute to the completer sample. Any patient who misses 3 consecutive scheduled rTMS sessions is withdrawn from the study. The fully adherent sample is a subgroup of the completer sample. This group comprises all patients who completed without a significant protocol violation. Significant protocol violations would include equipment malfunction or any reason a session is cancelled, reported and limited use of a prohibited pharmacological agent or illicit drug, etc. In addition, fully adherent patients can reschedule at most 2 sessions during the treatment phase.
- 3) Significance testing: All tests will be two-sided, performed at significance α =0.05, except where noted.
- 4) Preliminary analysis: All variables will be examined for outliers at all time points using multivariate and univariate techniques before specific statistical models described below are applied in hypotheses testing of interest. The distributions of all continuous variables will be checked for normality, and transformations will be employed, if necessary, before applying specific parametric techniques. The distribution of demographic and diagnostic characteristics at baseline in the two treatment arms will be examined and described in terms of means, standard deviations, proportions and 95% confidence intervals.

- 5) Adjustment for covariates: Hypotheses testing will be based on models that adjust for the prespecified covariates (specifically variable medication resistance, duration of current episode and age). This adjustment will be based on the inclusion of main effects for the covariate and interactions of treatment with each of these covariates. The models that study the longitudinal trajectory of symptoms severity will include also the 2-way interaction covariate*time and the 3-way interaction terms treatment*time*covariate. Interaction terms that are not significant will be omitted. The main covariate effects will always be maintained in the models whether or not they are significant. In our experience, the association between age and medication resistance has been weak and has not presented colinearity problems. Thus, no co-linearity problems are expected with these models. All analyses performed to investigate the effect of demographic and baseline diagnostic characteristics that have been found to be imbalanced with respect to site and/or treatment group will be considered exploratory, since no a priori hypotheses are stated.
- 6) Statistical Rules: The conduct of new statistical analyses that have not been planned in advance will be discussed with the DSMB and must be DSMB approved.

Hypothesis testing

1) Primary clinical hypothesis: Repeated daily rTMS delivered in a synchronized fashion (SYNC) over the duration of the randomized phase ("fixed" plus "variable length" components) results in superior clinical outcome compared to conventional non-synchronized (NON-SYNC) TMS.

Primary analysis of this hypothesis will be based on the primary outcome measure remission status. A logistic regression model will model the odds for response as a function of treatment condition. The model will adjust for medication resistance, episode duration and age. If no interaction term between treatment and any of the covariates is significant, the treatment effect will be interpreted in terms of the odds ratio for remission for SYNC rTMS vs. NON-SYNC rTMS. If an interaction between treatment and any of the covariates is statistically significant, we will interpret the interaction accordingly in terms of ratio of the odds ratios for remission for SYNC rTMS vs. NON-SYNC rTMS between two different levels of the covariate factors.

We will employ additional exploratory analyses merging selected aspect from the fMRI or EEG dataset to potentially be able to predict remitters based on baseline MRI characteristics or the amount of correctly timed EEG pulses delivered.

Approaches to Trial Conduct and Quality Control – This study is designed to be an effectively randomized, rigorously conducted trial of SYNC versus NON-SYNC TMS for depression. It builds on and takes advantage of the infrastructure and resources in place at the MUSC BSL from prior studies, including the OPT-TMS trial.

General Approach to Data Management –[name] and the BSL members, working with other MUSC resources (e.g. SC Clinical and Translational Research Institute (SCTR)) will be responsible for data management activities of this trial. The MUSC BSL has extensive experience with all aspects of data management for single and multicenter clinical trials.

The following section describes the proposed data management plan.

Database Creation and Documentation: The OPT-TMS study pioneered a system at MUSC that allows for easy web-based design, validation and maintenance of the core clinical database. The database will be developed using REDCAP, working with SCTR staff and statisticians and clinical trialists. The REDCAP database will have extensive data consistency checks programmed.

Data collection/data entry – data is entered directly into a REDCAP database via ipad while interviewing subject. Before final locking of the database, all entries will be checked by MUSC staff. Any deficiencies are resolved via Data Clarification Requests.

Data Quality Assurance. Data quality will be monitored on two levels: 1) as reported on the CRF (accuracy); 2) as entered into the study database (precision). For the former, all primary, secondary and safety data will be source document verified, and all CRF's will be visually inspected by the clinical staff before archiving. In addition, extensive edit checks will be programmed into REDCAP. Finally, independent quality assurance / quality control will be performed including a 20% random sample CRF to database data listing review.

Systems Environment and Security. All information systems used by MUSC in the management and storage of clinical trial data are housed on site in Brain Stimulation Lab. These offices are locked during non-business hours; entry to the building from the street can only be gained through the use of the touch pad entry lock or with key for the fire exit. A regular university foot and bike patrol officer patrols the building. MUSC's software security policy has three main components. The first component is antiviral protection: Corporate Edition Version 7.5 is being used to protect all servers and workstations from infection. Virus definitions are updated on a daily basis. The second component is password policies. Oracle, Clintrial, Access and Windows all include password protection features to prevent unauthorized access. These are all activated and kept fully functional by the IS department. System and Administrator level passwords are changed on a regular basis to enhance security. In addition to anti-virus software and password protection, two levels of firewall protection comprise the third component. The Medical University of South Carolina (MUSC) maintains firewall protection between the university and outside computer systems.

Backup Policy. The backup schedule consists of full-verified backups performed nightly.

Reports to Designated Data Safety Monitoring Board. The Data Safety and Monitoring Board (DSMB) will receive reports produced by the BSL at 6-month intervals on study progress, efficacy, and safety. A template for the report will be submitted to the DSMB for its input. Additional study-specific information not already in the template will be incorporated into the report as requested by the DSMB.

Randomization will be performed automatically by a software program using an encrypted randomization table on the computer attached to the TMS machine and backed up on MUSC Box. Personnel at MUSC will have no access to this randomization table, but personnel at Columbia University, who have no contact with subjects or access to primary clinical data, will be performing ongoing quality control. The randomization application will assign to each newly randomized subject a blinded designation of SYNC or Non-SYNC. The interface computer that drives the TMS machine will then operate either in a manner that synchronizes the treatment with the patient's EEG, or delivers non-synchronized TMS (identical frequency but randomized phase

Primary Clinical data will not leave MUSC. Processed MRI and EEG, de-identified data, will be analyzed by colleagues at Columbia University. Data will be transferred using MUSC Box, with subject number only and no other identifying information. The Columbia group will not get any data other than EEG and MRI files and the research number of the participant. They will never get other protected health information.

13.0 Provisions to Monitor the Data to Ensure the Safety of Subjects (if applicable)

There are 3 areas in which safeguards to protect subjects from undue risk require discussion. These include the procedures used to obtain informed consent, the procedures used to ensure confidentiality of the subjects' data, and the procedures used to minimize possible risks associated with the treatment procedures.

Informed Consent. In the consent forms and discussions with an investigator, patients are advised fully of the procedures to be used, the amount of time required of them, the fact that this study involves random assignment to two forms of TMS, only one of which has been tried before, the nature of the study and follow-up, the research procedures that will be conducted, the possible risks and benefits of the procedures, their right to refuse participation in the study without prejudice, their right to terminate participation at any moment without prejudice, and the name and telephone number of the Principal Investigator. All subjects will be required to have capacity to consent.

Confidentiality of Subjects' Responses. In the informed consent form, subjects are told that the information they provide and all findings will be kept strictly confidential, with access limited to the research staff at the research sites and the possible exception of state or federal regulatory personnel. No one but the project staff has access to the master list linking subjects' names to code numbers, and all information obtained is coded. The respective master lists are kept under strict lock and key at MUSC and with restricted access in Redcap.

Research Procedures. We have described above the potential risks of the research procedures. If the patient shows deterioration in their clinical status, we will stop him/her from proceeding in the study, and coordinate appropriate follow-up care with the referring psychiatrist. Certified TMS operators will visually determine the motor threshold using parameter estimation by sequential testing (PEST). We will minimize the risk of seizure by prescreening patients with an MRI scan of the head, and will tailor each person's stimulation parameters to their own motor (and indirectly seizure) threshold. We will exclude patients on all psychotropic medications (except for lorazepam at no greater than 3 mg/d) and all stimulants (except for caffeine). These could potentially lower the seizure threshold. We will minimize hearing damage by having all patients wear earplugs to protect their hearing during the TMS and MRI sessions. We will minimize the anxiety due to the MRI procedure by offering patients a mirror to look outside the bore at a screen and provide continuous feedback and update of procedure to patients in the scanner. All magnetically sensitive objects such as credit cards and electronic devices such as hearing aids, watches, and calculators will be put in a container to prevent damage from the magnet. The patient will be stimulated in clinical settings designed for TMS. An Ambu bag will be available. Patients will place earplugs in their ears.

Participation in the study will be treated as confidential, as will all records. The Food and Drug Administration and Institutional Review Board will have access to the records, but patients will be assigned study numbers for record keeping purposes. We will protect the identity of our patients by keeping the data in file cabinets in the PI's locked office, to which only they have a key.

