4.0 Study Endpoints (if applicable)

Remission, as defined by HRSD24 <10.

Safety will be assessed by using information on all relevant adverse events experienced, as well as pre- and post- primary treatment testing of cognitive functions and fMRI studies to determine target engagement.

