8. No history of failing to respond to an adequate course of ECT in this or any episode, and no ECT within the past 3 months	ATHF and physician evaluation
9. No contraindication to MRI	Physician evaluation; medical history
10. No contraindication to rTMS (history of neurological disorder or seizure (except induced by ECT), increased intracranial pressure, brain surgery, or head trauma with loss of consciousness for >15 minutes, implanted electronic device, metal in the head, or pregnancy)	Physician evaluation; medical history; MRI; urine pregnancy test
11. No unstable autoimmune, endocrine, viral, or vascular disorder. No unstable cardiac disease, uncontrolled hypertension, or sleep apnea	Physician evaluation; medical history
12. No active suicidal intent or plan, or history of attempt within the past 12 months	Physician evaluation
13. Willing to provide informed consent	

Patients with unipolar major depression meeting the above criteria will be enrolled. The baseline HRSD score (24-item) must be >20. To ensure that baseline levels of depression severity are stable at the time of study enrollment, patients will be dropped if they show > 30% improvement in the HRSD score from the time of initial intake (e.g., screening) to the baseline assessment.

All subjects will have an MRI scan after obtaining consent but before being randomized.

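### The primary remission model leaves out baseline HRSD24; the planned test is valid, but a modest amount of power and prespecified adjustment for severity are forgone

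*Combined protocol and SAP*

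**What the plan says.** The endpoint in section 4.0 is "Remission, as defined by HRSD24 <10". Section 12.0, item 5, names the covariates for hypothesis testing as "specifically variable medication resistance, duration of current episode and age". The primary logistic model repeats them: "The model will adjust for medication resistance, episode duration and age". Item 5 also sets their form: "This adjustment will be based on the inclusion of main effects for the covariate and interactions of treatment with each of these covariates". Non-significant interactions are then dropped, and main effects always stay.

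The baseline score exists for everyone. Section 5.0 states "The baseline HRSD score (24-item) must be >20" (Table E.1 has 20 or more), and "patients will be dropped if they show > 30% improvement in the HRSD score from the time of initial intake" to the baseline assessment.

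Section 12.0 describes allocation from a computer-held randomisation table and states no stratification by severity. Under item 5, analyses of baseline "characteristics that have been found to be imbalanced with respect to site and/or treatment group will be considered exploratory". Item 6 adds: "The conduct of new statistical analyses that have not been planned in advance will be discussed with the DSMB and must be DSMB approved".

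**The concern.** With an absolute cut-off, the improvement needed depends on where the patient starts. A patient entering at 21 must fall by (21 − 9)/21 = 57% to score 9. One entering at 30 must fall by (30 − 9)/30 = 70%. The entry score is therefore a natural covariate for this endpoint, and it is absent from a model that already adjusts for three others.

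The plan treats analyses of baseline imbalances as exploratory. That is sound practice, but it means that adjustment for severity can reach the primary estimate only if it is written in beforehand. At stake is some efficiency in a comparison of about 30 patients per arm that is meant to inform a go/no-go decision.

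**Working it through.** **Inputs.** From section 12.0: 60 randomised 1:1; 50 or 54 completers (both figures appear); two-sided alpha 0.05; about 30% remission in open-label TMS trials and roughly 60% for ECT, read here as the two arms' rates. Assumed, because the documents do not give them: r, and a joint R² of 0.09 for the three planned covariates.

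**1. The plan's own power figure.** Section 12.0 states 0.95 for a chi-square test with 50 completers. Power = Φ{[|p₁ − p₂|√n − 1.96√(2p̄q̄)] / √(p₁q₁ + p₂q₂)}.

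- 25 per arm: (0.3 × 5 − 1.96 × 0.7036)/0.6708 = 0.18, so power is 0.57.
- 30 per arm: (1.643 − 1.379)/0.6708 = 0.39, so power is 0.65.

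The 0.95 is not reproduced at these rates. The figure behind it is not shown, so its inputs cannot be checked. That is a separate matter; here it only sets the starting level.

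**2. Power without and with baseline HRSD24.** Simulation with a normal latent endpoint, 30% versus 60%, main-effects logistic model, Wald test, 12,000 runs per cell (Monte Carlo SE 0.004), 30 per arm:

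| r | Baseline independent of the three covariates | Baseline correlated 0.3 with two of them |
|---|---|---|
| 0 | 0.671 / 0.670 | – |
| 0.2 | 0.682 / 0.689 | – |
| 0.3 | 0.668 / 0.691 | 0.671 / 0.683 |
| 0.5 | 0.668 / 0.740 | 0.669 / 0.719 |

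The gain is under 1 point up to r = 0.2, 1 to 2 points at r = 0.3 and 5 to 7 points at r = 0.5. At 25 per arm, with independence, the pairs are 0.583 / 0.608 (r = 0.3) and 0.586 / 0.646 (r = 0.5). Screening the three planned interactions first does not change the gain (0.672 / 0.694 and 0.671 / 0.743 at 30 per arm).

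**3. Type I error** (45% in both arms, 20,000 runs per cell, 25 to 30 per arm). The Wald test gives 0.052–0.056 without baseline and 0.052–0.058 with it. The new term does no material harm.

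**4. Chance imbalance, 30 per arm.** The SE of the standardised baseline difference is √(2/30) = 0.258. The probability of a difference above 0.25 SD is 2[1 − Φ(0.25/0.258)] = 33%; above 0.5 SD it is 5%. With z = Φ⁻¹(0.45), a 0.25 SD difference d shifts the remission difference by Φ(z + rd/2) − Φ(z − rd/2). This is 1 point at r = 0.1, 3 at r = 0.3 and 5 at r = 0.5. The 95% CI half-width is 1.96√(2 × 0.45 × 0.55/30) = 25.2 points.

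**5. Effect on the two estimates.**

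- *Odds ratio* (30 per arm, 30% versus 60%). The median log odds ratio rises from 1.44 to 1.58 (r = 0.3) or 1.81 (r = 0.5). Its median SE rises from 0.61 to about 0.66 or 0.72. The ratio goes from 1.44/0.61 = 2.36 to 1.58/0.66 = 2.39 or 1.81/0.72 = 2.51. Power therefore rises while the interval widens.
- *Standardised remission difference.* In large samples the half-width is multiplied by √{1 − [rφ(z)]²/(p(1 − p))}, which is 0.971 at r = 0.3 and 0.917 at r = 0.5. So 25.2 becomes 24.4 or 23.1 points, a narrowing of 0.8 or 2.1. Simulated at 30 per arm, the narrowing is about 0.5 or 1.8 points, with a slight widening at r = 0.

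**6. Remitters per term.** At 45% of 50 to 60 patients there are 22.5 to 27 remitters. That is 5.6–6.8 for each of the four present main-effect terms and 4.5–5.4 for each of five. If both arms remit at 30%, there are 15 to 18 remitters, or 3.0–3.6 for each of five.

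**The case against.** The strongest reply is that nothing here is an error. The three covariates are prespecified and always retained. Section 5.0 discusses medication resistance, chronicity and age as influences on response, and does not single out baseline severity as a predictor. The benefit rests on an r that nobody has supplied. The entry floor and the rule on improvement of more than 30% may narrow the baseline range and lower r. At r = 0.3 with overlapping covariates the gain is about 1 point. Sections 1.0 and 12.0 describe an early-phase comparison, not a definitive trial, and an exploratory severity analysis remains open.

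Much of this stands: the plan is valid, the gain may be nil, and no go/no-go decision is shown to turn on it. It does not remove the case for a change that needs no new data, because an exploratory analysis cannot alter the primary estimate.

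Three stronger inferences are not supported:

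- **That the primary test is biased or invalid without baseline.** Randomisation protects it, and chance imbalance is already covered by its error rate and confidence interval.
- **That item 5 is at fault for calling analyses of imbalances exploratory.** That is proper discipline.
- **That adjustment would sharpen the odds ratio, which is the plan's stated measure.** Its standard error rises. A raw remission difference would gain nothing either; only a difference standardised from the adjusted model does.

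**Conclusion.** The omission is real and worth correcting as an inexpensive improvement, not as a defect that undermines the trial. At 30 per arm and 30% versus 60%, the loss of power is about nil at r = 0 to 0.2, 1 to 2 points at r = 0.3 and 5 to 7 points at r = 0.5. The lower figures apply if baseline severity overlaps with the planned covariates. The standardised difference would have a 95% CI narrower by at most about 2 points on a half-width near 25.

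These figures rest on the assumed r, the assumed covariate strength, a normal latent score, and the reading of 30% and 60% as the two arms' rates. They also assume that baseline and endpoint come from the same 24-item scale. The omission does not account for the gap between the stated 0.95 power and the recomputed figures.

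**What to change.** Before unblinding, amend section 12.0 as follows.

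1. Add continuous baseline HRSD24 as a prespecified main effect in the primary logistic model. State that it carries no treatment interaction, since item 5 would otherwise add one.
2. Report beside the adjusted odds ratio a remission difference obtained by marginal standardisation from that model, with a delta-method or bootstrap 95% CI. Section 12.0 already undertakes to report differences in remission.
3. Confirm that baseline and endpoint scores use the same 24-item scale. Sections 3.0 and 10.0 list a 28-item Hamilton scale for the weekly ratings, against 24 items for entry and endpoint, and these must be reconciled.

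The cost is SAP wording and one model term. Item 6 requires DSMB discussion and approval for unplanned analyses, so the change should be made before any imbalance is seen. The SAP should state the downsides: a larger conditional odds ratio with a wider interval, and fewer remitters per term (4.5–5.4 at 45% remission, 3.0–3.6 at 30% in both arms). The choice between Wald and likelihood-ratio tests is a separate matter.

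### The primary SYNC versus NON-SYNC odds ratio is promised only if three interaction tests are all non-significant; otherwise the plan names no overall test of superiority

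*Combined protocol and SAP*

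**What the plan says.** All references are to Section 12.0 of the combined protocol and SAP unless stated.

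- **Hypothesis.** The primary clinical hypothesis is that SYNC rTMS "results in superior clinical outcome compared to conventional non-synchronized (NON-SYNC) TMS". The primary outcome is remission status, analysed by logistic regression adjusted for medication resistance, episode duration and age.
- **Interactions.** Item 5 (Adjustment for covariates) adds an interaction of treatment with each of the three covariates, then prunes: "Interaction terms that are not significant will be omitted". Covariate main effects always stay in.
- **Level.** Item 3 gives one rule, "All tests will be two-sided, performed at significance" level 0.05 except where noted. No separate level is noted for interactions.
- **First branch.** "If no interaction term between treatment and any of the covariates is significant, the treatment effect will be interpreted" as the SYNC versus NON-SYNC odds ratio for remission.
- **Second branch.** If any interaction is significant, that interaction is interpreted "in terms of ratio of the odds ratios for remission for SYNC rTMS vs. NON-SYNC rTMS between two different levels of the covariate factors". Nothing further is specified.
- **Population.** "The main analysis will focus on the intent-to-treat (ITT) sample".
- **Elsewhere.** The power statement rests on a "simple chi-square comparison of remitters across the two groups", and the same text promises to report the differences in remission. Section 1.0 states an interest in the overall comparison and says the study will inform a go/no-go decision on a full trial.

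**The concern.** The hypothesis, the power statement and the go/no-go use all concern one two-group comparison of remission. The plan commits to that comparison only if three secondary tests come out a particular way. In the other branch the committed quantity answers a different question: whether the SYNC effect differs between, say, younger and older patients. It carries no information on whether SYNC beats NON-SYNC overall.

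In that branch the plan names no overall estimate, no covariate values at which the arms are compared, and no centring of covariates. An analyst could reasonably report the main-effects odds ratio, the treatment coefficient of the final model, or an unadjusted chi-square, and the plan does not choose among them. What is at stake is a committed primary answer.

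**Working it through.** **1. What the second-branch quantity contains.** Take a retained age interaction: logit P(remission) = b0 + b1·T + b2·age + b3·T·age + other covariates.

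- Log odds ratio for SYNC at age a: b1 + b3·a.
- Ratio of odds ratios between ages a1 and a2: exp[b3·(a2 − a1)].

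The second expression does not contain b1. Its value is the same whether SYNC is better, worse or equal overall, so it cannot test superiority. If age is not centred, b1 is the effect at age 0, while eligible patients are 21 to 70 (Section 5.0).

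**2. Does another part of the plan supply the overall test?**

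- The chi-square is the basis of the power figure. It is not named as the primary or fallback analysis, and it is unadjusted.
- The promised remission differences are descriptive, with no test attached.
- Item 6 says: "The conduct of new statistical analyses that have not been planned in advance will be discussed with the DSMB and must be DSMB approved". That is a route for approving an addition; it does not specify one.

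**3. The plan's own figure.** The stated power is 0.95 with 50 completers. Reading the quoted rates of about 30% (rTMS) and about 60% (ECT) as the contrast, with 25 per arm and two-sided 0.05:

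- null SE = √(2 × 0.45 × 0.55 / 25) = 0.1407
- alternative SE = √((0.3 × 0.7 + 0.6 × 0.4) / 25) = 0.1342
- z = (0.30 − 1.96 × 0.1407) / 0.1342 = 0.18, so power is about 57% (65% with 30 per arm)

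The 0.95 is not reproduced. Fig 1D, which may show its inputs, is not in the available text. This is a separate matter, and the present point does not depend on it.

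**4. How often a trial enters the second branch with no true interaction.** For three independent tests at 0.05: 1 − 0.95³ = 14.3%. Simulation of the planned model, 1:1 allocation, one term per covariate, 3,000 trials per scenario, independent standard normal covariates without effect on remission:

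| n | Remission rates | Any interaction, Wald | Any interaction, likelihood ratio |
|---|---|---|---|
| 60 | 30% / 30% | 14.2% | 20.4% |
| 60 | 30% / 60% | 14.7% | 19.7% |
| 60 | 45% / 45% | 15.7% | 20.5% |
| 54 | 30% / 30% | 14.3% | 22.5% |
| 54 | 30% / 60% | 13.8% | 21.2% |

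With uniform covariates instead (resistance 1-4, duration 1-36 months, age 21-70; 10,000 trials per scenario), Wald rates were 14.5-16.5% at n=60 and 14.7-15.5% at n=54. Giving each covariate an effect of 0.4 log-odds per SD moved them to 13.2-14.4% at n=60. Further likelihood-ratio runs at n=54-60 gave values from 18%.

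**5. Cost to the primary answer.** At 30% versus 60%:

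| n | Overall odds ratio always tested | Reached under the rule (Wald) and significant |
|---|---|---|
| 60 | about 64-65% | about 55% |
| 54 | about 60% | about 52% |

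The arithmetic agrees: 0.65 × (1 − 0.15) = 0.55. With a likelihood-ratio diversion rate near 20% it would be roughly 0.65 × 0.80 = 0.52. Among diverted trials, 59-64% had a significant main-effects SYNC odds ratio. That is roughly the trial's ordinary power, so diversion is close to unrelated to the overall result.

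**6. Type I error.** With equal remission in the arms, the uniform-covariate runs gave 5.1-5.5% for the main-effects model and 5.2-5.6% for the single-odds-ratio path.

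**7. Does the choice of overall reading matter?** With uncentred covariates, the final-model treatment coefficient disagreed with the main-effects model on significance in about 49-61% of diverted trials (n=60). With centred covariates, committing to either costs nothing: power at 30% versus 60%, n=60, was 64.7% for the main-effects model and 65.3% for the centred final-model term.

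**The case against.** The strongest reply is that the overall comparison is not really lost. The plan promises the remission differences without condition, a treatment term can always be computed, and reading a significant interaction before a main effect is conventional. If a real interaction exists, a single overall odds ratio may mislead. Section 1.0 says this is not a formal efficacy trial, and Section 12.0 says it is not meant to be definitive.

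Most of this stands, and it limits the point. The loss is of a pre-specified primary test, not of data. But a descriptive difference is not a test of the stated superiority hypothesis, and the interaction can still be read and reported beside a fixed primary result.

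A reader might infer more than the documents support:

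- **That the rule inflates false positives.** It does not (step 6).
- **That the plan forbids an overall odds ratio.** It is silent; it does not prohibit one.
- **That the missing go/no-go criterion results from this branch.** No numerical criterion is given anywhere, so that gap applies equally to the first branch.
- **That an overall test would necessarily be chosen after the interaction results are known.** Item 6 sets no timing, and allocation stays concealed until the dataset is locked, so the gap can still be closed beforehand.
- **That the 59-64% significant among diverted trials is an added harm.** It only reflects the trial's ordinary power under the assumed rates.

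**Conclusion.** The point holds as a gap created by a stated rule: the primary odds ratio is conditional on three interaction tests, and the alternative branch has no committed test of superiority. By chance alone, about 14-16% of trials at n=54-60 would enter that branch with Wald tests, and about 18-23% with likelihood-ratio tests. At 30% versus 60% and n=60, the chance of a committed, significant overall result falls from about 65% to about 55% with Wald tests.

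These figures assume no true interaction, one model term per covariate (a categorical resistance variable would add terms) and the covariate distributions given above. The 60% SYNC rate is also an assumption, since the plan quotes it for ECT. The reading of the text needs none of these. The change should be made, but the early-phase, non-definitive purpose keeps it below a critical defect.

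**What to change.** Amend items 5 and the primary-hypothesis text of Section 12.0, dated before unblinding:

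1. The primary p-value and odds ratio with 95% CI come from the treatment term of one main-effects logistic model in the ITT sample (remission on treatment, medication resistance, episode duration and age), whatever the interactions show. Exempt this model from the interaction-pruning rule.
2. Report a risk difference with 95% CI separately, because a logistic treatment coefficient does not yield one. Use either standardisation (marginal predictions) from the same model with a delta-method or bootstrap interval, or the unadjusted proportions.
3. Report the three treatment-by-covariate interactions, with centred covariates and a named test (Wald or likelihood ratio), as exploratory response-predictor analyses that cannot replace the primary result.

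The cost is SAP wording only: no new data, no extra model terms in the primary analysis and no loss of power. The stated interest in response predictors is kept.
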